**B26. In the last month, have you dealt drugs? [dealt\_fu]**

- Yes
- No
- DK/R

**B27. If *dealt\_fu* = "yes": What is the main reason you've dealt drugs? (Read out list; check only one) [dealw\_fu]**

- Income for drugs
- Income for other purposes
- To clear debts
- For food or shelter
- Another reason
- DK/R

**B27a. If *dealw\_oth\_fu* = "another reason": What is the main reason you've dealt drugs: \_\_\_\_\_ [dealw\_oth\_fu]**

BROWN

School of Public Health

**B28. If dealt\_fu= "yes": In the last month, have you dealt drugs that you suspected or knew had fentanyl in them? [fentdeal\_fu]**

Yes

No

DK/R

**B29. If dealt\_fu= "yes": Are you concerned about fentanyl contaminating your supply? [fentdeal\_concern\_fu]**

Very concerned

A little concerned

Neutral

Not concerned

DK/R

**B30. If dealt\_fu= "yes": If given the choice, would you prefer not to deal drugs that had fentanyl in them? [fentindrg\_fu]**

Very concerned

A little concerned

Neutral

Not concerned

DK/R

## **SECTION C: FENTANYL**

*Interviewer prompt: Now we are going to ask you questions about fentanyl. Please answer True, False, or Don't know/Refuse for the next 6 questions.*

**C1. Fentanyl is an opioid [info1\_fu]**

- True
- False
- DK/R

**C2. Fentanyl is not as strong as heroin [info2\_fu]**

- True
- False
- DK/R

**C3. Fentanyl acts more quickly than heroin [info3\_fu]**

- True
- False
- DK/R

**C4. Drugs that are mixed with fentanyl look different than drugs that are not mixed with fentanyl [info4\_fu]**

- True
- False
- DK/R

**C5. Someone is more likely to overdose when using drugs that contain fentanyl than when using drugs that do not contain with fentanyl [info5\_fu]**

- True
- False
- DK/R

**C6. In Rhode Island, fentanyl now causes more overdoses than heroin [info6\_fu]**

- True
- False
- DK/R

**C7. In the last month, have you been prescribed fentanyl by a doctor? [fentr xm1\_fu]**

- Yes
- No
- DK/R

**C8. If fentr xm1\_fu= "yes": In what forms have you been prescribed fentanyl? (Read out list; check all that apply) [fentform\_fu]**

- Skin patch [1]
- Pills [2]
- Nasal spray [3]
- Lozenge/lollipop [4]
- A film that dissolves under your tongue [5]
- A spray that goes under your tongue [6]
- Other: [7]
- DK/R [99]

**C8a. If fentform\_fu= "other": In what forms have you been prescribed fentanyl: \_\_\_\_\_ [fentform\_oth\_fu]**

**C9. If fentr xm1\_fu= "yes": In the last month, have you used prescription fentanyl in a way that was not prescribed by a doctor (without a prescription, or different route or different dose than as prescribed by a doctor)? [fentnorx\_fu]**

- Yes
- No
- DK/R

**C10. If fentnorx\_fu= "yes": In the last month, how often have you used prescription fentanyl in a way that was not prescribed by a doctor? [fentdiv6\_fu]**

- Never
- Once or a couple of times
- About once a month
- At least every week
- Every day
- DK/R

**C11. If fentnorx\_fu= "yes": In the last month, what forms of prescription fentanyl have you used in a way that was not prescribed by a doctor? (Read out list; check all that apply) [fentdivform\_fu]**

- Skin patch [1]
- Pills (orally) [2]
- Nasal spray [3]
- Injecting [4]
- Snorting [5]
- Smoking [6]
- Lozenge/lollipop [7]
- A film that dissolves under your tongue [8]

Page 99 of 144

Brown University IRB Original Approval: 04/18/2019

Brown University IRB Amendment Approval: 11/22/2020

Brown University IRB Amendment Approval: 08/10/2020

Brown University IRB Amendment Approval: 10/15/2020

Brown University IRB Amendment Approval: 02/26/2021

Brown University IRB Continuing Review Approval: 03/18/2021

Brown University IRB Amendment Approval: 06/15/2021

Brown University IRB Amendment Approval: 09/01/2021

Brown University IRB Amendment Approval: 10/05/2021

Brown University IRB Amendment Approval: 10/15/2020

Brown University IRB Amendment Approval: 02/26/2021

Brown University IRB Continuing Review Approval: 03/18/2021

Brown University IRB Amendment Approval: 06/15/2021

Brown University IRB Amendment Approval: 09/01/2021

Brown University IRB Amendment Approval: 10/05/2021

BROWN

School of Public Health

Brown University IRB Amendment Approval: 11/09/2021

Brown University IRB Amendment Approval: 12/13/2021

Other: [77]

DK/R [99]

**C11a.** If *fentdivform\_fu*= “other”: **In the last month, what forms of prescription fentanyl have you used in a way that was not prescribed by a doctor:** \_\_\_\_\_ [*fentdivform\_oth\_fu*]

**C12.** If *fentnorx\_fu*= “yes”: **In the last month, how did you get fentanyl without a prescription?** (Read out list; check all that apply) [*fentbuy\_fu*]

Purchased from a dealer or on the street [1]

A close friend [2]

A casual friend or acquaintance [3]

A sex partner [4]

An immediate family or household member [5]

An extended family member [6]

Purchased from the internet or “dark web” [7]

Other: [77]

DK/R [99]

**C12a.** If *fentbuy\_fu*= “other”: **In the last month, who did you get fentanyl without a prescription:** \_\_\_\_\_ [*fentbuy\_oth\_fu*]

*Interviewer prompt: Now we are going to be talking about drugs that contained fentanyl. For example, you thought you were buying heroin, but it was contained fentanyl.*

**C13.** **In the last month, how often have you used fentanyl or drugs you were confident contained fentanyl?** [*fentfreq\_fu*]

Never

Once or a couple of times

About once a month

At least every week

Every day

DK/R

**C14.** If *fentfreq\_fu* <> “never” or “DK/R”: **What drugs have you used that you were confident contained fentanyl in the past... (Read out list; check all that apply)** [*fentdrgconf\_fu*]

		Past month (Y/N)	Past 7 days (Y/N)	Past 3 days (Y/N)

Page 100 of 144

Brown University IRB Original Approval: 04/18/2019

Brown University IRB Amendment Approval: 11/22/2020

Brown University IRB Amendment Approval: 08/10/2020

Brown University IRB Amendment Approval: 10/15/2020

Brown University IRB Amendment Approval: 02/26/2021

Brown University IRB Continuing Review Approval: 03/18/2021

Brown University IRB Amendment Approval: 06/15/2021

Brown University IRB Amendment Approval: 09/01/2021

Brown University IRB Amendment Approval: 10/05/2021

Brown University IRB Amendment Approval: 10/15/2020

Brown University IRB Amendment Approval: 02/26/2021

Brown University IRB Continuing Review Approval: 03/18/2021

Brown University IRB Amendment Approval: 06/15/2021

Brown University IRB Amendment Approval: 09/01/2021

Brown University IRB Amendment Approval: 10/05/2021

BROWN

School of Public Health

Brown University IRB Amendment Approval: 11/09/2021

Brown University IRB Amendment Approval: 12/13/2021

C14a	Marijuana or hash oil, including edibles and synthetic marijuana			
C14b	Club drugs such as Molly, MDMA, Ecstasy, GHB, Ketamine OR Molly/MDMA/Ecstasy [MO]			
C14c	Psychedelics, such as Mushrooms, Acid, LSD, DMT OR Mushrooms [MU]			
C14d	Crystal methamphetamine (crystal meth, tina, crank, ice)			
C14e	Powder cocaine			
C14f	Crack cocaine			
C14h	Heroin			
C14j	Prescription Opioid Pills (Vicodin, Percocet, etc.)			
C14k	Prescription Benzodiazepines (Xanax, Klonopin, etc.)			
C14l	Prescription Stimulants (Adderall, Ritalin, etc.)			
C14m	Other:			
C14n	DK/R			

**C15. If fentfreq\_fu <> "never" or "DK/R": The last time you used a drug you were confident contained fentanyl, did you know that the drug that contained fentanyl before you used it? [fentconf\_fu]**

Yes

No

Page 101 of 144

Brown University IRB Original Approval: 04/18/2019

Brown University IRB Amendment Approval: 11/22/2020

Brown University IRB Amendment Approval: 08/10/2020

Brown University IRB Amendment Approval: 10/15/2020

Brown University IRB Amendment Approval: 02/26/2021

Brown University IRB Original Approval/Continuing Review Approval: 03/18/2021

Brown University IRB Amendment Approval: 06/15/2021

Brown University IRB Amendment Approval: 09/01/2021

Brown University IRB Amendment Approval: 10/05/2021

Brown University IRB Amendment Approval: 10/15/2020

Brown University IRB Amendment Approval: 02/26/2021

Brown University IRB Continuing Review Approval: 03/18/2021

Brown University IRB Amendment Approval: 06/15/2021

Brown University IRB Amendment Approval: 09/01/2021

Brown University IRB Amendment Approval: 10/05/2021

**BROWN**  
School of Public Health

Brown University IRB Amendment Approval: 11/09/2021

Brown University IRB Amendment Approval: 12/13/2021

DK/R

**C16. If fentfreq\_fu <> "never" or "DK/R": The last time you used a drug you were confident contained fentanyl, why were you confident that it contained fentanyl? (Read out list; check all that apply) [fentwhy\_fu]**

- A dealer told me [1]
- A sex partner told me [2]
- A friend told me [3]
- I overdosed [4]
- A sex partner overdosed [5]
- A friend overdosed [6]
- I had a bad reaction [7]
- Quicker onset of high [8]
- Different high [9]
- Differences in appearance, smell or taste [10]
- Other: [77]
- DK/R [99]

**C16a. If fentwhy\_fu= "Other": The last time you used a drug you were confident contained fentanyl, why were you confident that it contained fentanyl: \_\_\_\_\_ [fentwhy\_oth\_fu]**

**C17. The last time you used a drug that you were confident contained fentanyl, how did you get it? [fentobt\_fu]**

- Purchased from a dealer or on the street
- A close friend
- A casual friend or acquaintance
- A sex partner
- An immediate family or household member
- An extended family member
- Purchased from the internet or "dark web"
- Other
- No
- DK/R

**C17b. If fentobt\_fu = "other": The last time you used a drug that you were confident contained fentanyl, how did you get it: \_\_\_\_\_ [fentobt\_why\_fu]**

**C18. The last time you used a drug you were confident contained fentanyl, what did you do when you found out you? (Read out list; check all that apply) [skill1\_fu]**

- Took them as I usually would [1]
- Threw them out [2]

Page 102 of 144

Brown University IRB Original Approval: 04/18/2019

Brown University IRB Amendment Approval: 11/22/2020

Brown University IRB Amendment Approval: 08/10/2020

Brown University IRB Amendment Approval: 10/15/2020

Brown University IRB Amendment Approval: 02/26/2021

Brown University IRB Original Approval: Spring 2019 Review Approval: 03/18/2021

Brown University IRB Amendment Approval: 06/15/2021

Brown University IRB Amendment Approval: 09/01/2021

Brown University IRB Amendment Approval: 10/05/2021

Brown University IRB Amendment Approval: 10/15/2020

Brown University IRB Amendment Approval: 02/26/2021

Brown University IRB Continuing Review Approval: 03/18/2021

Brown University IRB Amendment Approval: 06/15/2021

Brown University IRB Amendment Approval: 09/01/2021

Brown University IRB Amendment Approval: 10/05/2021

BROWN

School of Public Health

Brown University IRB Amendment Approval: 11/09/2021

Brown University IRB Amendment Approval: 12/13/2021

Gave them away [3]  
 Sold them [4]  
 Went slower [5]  
 Used less [6]  
 Did a tester [7]  
 Used with someone else around [8]  
 Other: [77]  
 DK/R [99]

**C18a. If skill1\_fu= "other": The last time you used a drug you were confident contained fentanyl, what did you do when you found out: \_\_\_\_\_ [skill1\_oth\_fu]**

*Interviewer prompt: Now that we have asked you what you've done in the past when you had drugs that contained fentanyl, we would like to know more about what you do in the future.*

**C19. What would you do if you found out your drugs had fentanyl in them? (Read out list; check all that apply) [motiv1\_fu]**

Take them as I usually would [1]  
 Throw them out [2]  
 Give them away [3]  
 Sell them [4]  
 Go slower [5]  
 Use less [6]  
 Do a tester [7]  
 Use with someone else around [8]  
 Talk with the supplier or dealer [8]  
 Other [77]  
 DK/R [99]

**D19a. If motiv1\_fu = "Other": What would you do if you found out your drugs had fentanyl in them: \_\_\_\_\_ [motiv1\_oth\_fu]**

*Interviewer prompt: We would like to know your thoughts about the effects of fentanyl or drugs that have fentanyl in them. Please indicate how much you agree or disagree with the following statements:*

**C20. Fentanyl or drugs that have fentanyl in them are a better high than drugs that do not have fentanyl in them [precep1\_fu]**

Strongly disagree	Disagree	Neutral	Agree	Strongly agree	DK/R
-------------------	----------	---------	-------	----------------	------

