Purchased from the internet or "dark web" [7]

Other: [77]

DK/R [99]

**D12a.** If fentbuy= "other": In the last month, who did you get fentanyl without a prescription: \_\_\_\_\_ [fentbuy\_oth]

*Interviewer prompt: Now we are going to be talking about drugs that contained fentanyl. For example, you thought you were buying heroin, but it was contained fentanyl.*

**D13. I am confident that I have used a drug that contained fentanyl that was not sold as fentanyl.** [fentconfevr]

Strongly disagree	Disagree	Neutral	Agree	Strongly agree	DK/R
-------------------	----------	---------	-------	----------------	------

For responses *Strongly Disagree, Disagree, Neutral, DK/R* → skip to D19

**D14. In the last month, how often have you used fentanyl or drugs you were confident contained fentanyl?** [fentfreq]

Never

Once or a couple of times

About once a month

At least every week

Every day

DK/R

**D15. If fentfreq = "Once or a couple of times" or "About once a month" or "At least every week" or "Every day": What drugs have you used that you were confident contained fentanyl in the past... (Read out list; check all that apply) [fentconfevr]**

		Past month (Y/N)	Past 7 days (Y/N)	Past 3 days (Y/N)
D15a	Marijuana or hash oil, including edibles and synthetic marijuana			
D15b	Club drugs such as Molly, MDMA, Ecstasy, GHB, Ketamine OR Molly/MDMA/Ecstasy [MO]			
D15c	Psychedelics, such as Mushrooms, Acid, LSD, DMT OR Mushrooms [MU]			
D15d	Crystal methamphetamine (crystal meth, tina, crank, ice)			
D15e	Powder cocaine			
D15f	Crack cocaine			
D15h	Heroin			
D15j	Prescription Opioid Pills (Vicodin, Percocet, etc.)			
D15k	Prescription Benzodiazepines (Xanax, Klonopin, etc.)			
D15l	Prescription Stimulants (Adderall, Ritalin, etc.)			
D15m	Other:			

D15n	DK/R			
------	------	--	--	--

**D16. If fentfreq = "Once or a couple of times" or "About once a month" or "At least every week" or "Every day": The last time you used a drug you were confident contained fentanyl, did you know that the drug that contained fentanyl before you used it? [fentconf]**

Yes

No

DK/R

**D17. If fentfreq = "Once or a couple of times" or "About once a month" or "At least every week" or "Every day": The last time you used a drug you were confident contained fentanyl, why were you confident that it contained fentanyl? (Read out list, check all that apply) [fentwhy]**

A dealer told me [1]

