A sex partner told me [2]

A friend told me [3]

I overdosed [4]

A sex partner overdosed [5]

A friend overdosed [6]

I had a bad reaction [7]

Quicker onset of high [8]

Different high [9]

Differences in appearance, smell or taste [10]

Other: [77]

DK/R [99]

**D17a. If fentwhy= "Other": The last time you used a drug you were confident contained fentanyl, why were you confident that it contained fentanyl: \_\_\_\_\_ [fentwhy\_oth]**

**D17a. If fentfreq = "Once or a couple of times" or "About once a month" or "At least every week" or "Every day": The last time you used a drug that you were confident contained fentanyl, how did you get it? [fentobt]**

Purchased from a dealer or on the street

A close friend

A casual friend or acquaintance

A sex partner

An immediate family or household member

An extended family member

Purchased from the internet or "dark web"

Other

DK/R

**D17b. If fentobt = "other": The last time you used a drug that you were confident contained fentanyl, how did you get it: \_\_\_\_\_ [fentobt\_why]**

**D18. If fentfreq = "Once or a couple of times" or "About once a month" or "At least every week" or "Every day": The last time you used a drug you were confident contained fentanyl, what did you do when you found out you? (Read list out loud; check all that apply) [skill1]**

- Took them as I usually would [1]
- Threw them out [2]
- Gave them away [3]
- Sold them [4]
- Went slower [5]
- Used less [6]
- Did a tester [7]
- Used with someone else around [8]
- Other: [77]
- DK/R [99]

**D18a. If skill1= "other": The last time you used a drug you were confident contained fentanyl, what did you do when you found out: \_\_\_\_\_ [skill1\_oth]**

*Interviewer prompt: Now that we have asked you what you've done in the past when you had drugs that contained fentanyl, we would like to know more about what you do in the future.*

**D19. What would you do if you found out your drugs had fentanyl in them? (Read list out loud; check all that apply) [motiv1]**

- Take them as I usually would [1]
- Throw them out [2]
- Give them away [3]
- Sell them [4]
- Go slower [5]
- Use less [6]
- Do a tester [7]
- Use with someone else around [8]
- Talk with the supplier or dealer [8]
- Other [77]
- DK/R [99]

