Got naloxone [11]

Other [77]

DK/R [99]

**C39a. If skill1fentneg\_fu= "Other": What did you do when you found out you had drugs that did not contain fentanyl: \_\_\_\_\_ [skill1fentneg\_fu]**

**C40. If testneg\_fu= "yes": Did you experience any of the following unwanted negative reactions from using the drug that tested negative for fentanyl? (Read out list; check all that apply) [fentreactneg\_fu]**

Lost consciousness/blacked out [1]

Blue or gray lips or skin [2]

Seizure [3]

Had a hard time breathing [4]

Elevated breathing [5]

Stopped breathing [6]

Inability to talk [7]

Not responsive to stimulus (like having your name called or physical contact) [8]

Overheating [9]

Irregular heart beat (fast, slow, irregular or palpitations) [10]

Paranoia [11]

Can't remember getting high [12]

None [13]

Other [77]

DK/R [99]

**C40a. If fentreactneg\_fu= "Other": Did you have any of the following unwanted negative reactions from using the drug that tested negative for fentanyl: \_\_\_\_\_ [fentreactneg\_oth\_fu]**

**C43. Has fentanyl changed how you think about starting methadone or buprenorphine (Suboxone), or starting other forms of addiction treatment? [fentottrt\_neg]**

Yes, I accessed addiction treatment because of concerns about fentanyl

Yes, I am thinking about accessing treatment because of concerns about fentanyl (but haven't done so yet)

No

Already in some kind of addiction treatment

DK/R

**C44. Has fentanyl changed how you use drugs in any of the following ways? (Read out list; check all that apply) [fentchange\_fu]**

More likely to use with others [1]

More likely to inject slowly and/or taste drugs first [2]

More likely to use in public (e.g., outside) [3]

More likely to use in places where other people are around [4]

Less likely to use alone [5]

More likely to use where naloxone is available [6]

More likely to carry take-home naloxone [7]

Using less often and/or using smaller amount of drugs each time [8]

More likely to use drugs containing fentanyl [9]

More likely to use drugs unlikely to contain fentanyl (rather than drugs that may contain fentanyl) [10]

Other: [77]

Use hasn't changed [11]

DK/R [99]

**C44a. If fentchange\_fu= "More likely to use drugs unlikely to contain fentanyl: Specify drugs less likely to contain fentanyl: \_\_\_\_\_ [fentchange\_drg\_fu]**

Revised & Approved 11/22/2019

Revised & Approved 12/09/2019

Administrative correction submitted 12/12/2019

Revised & Approved 08/17/2020

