In two per-protocol sub-analyses, we will determine the effect of the intervention on the primary study endpoint among those who: (1) reported using fentanyl test strips during at least one intervention visit (months one, two, and three) compared to all participants assigned to the control arm; and (2) participants who completed one, two, and all three intervention visits using an ordinal variable, compared to all participants assigned to the control arm.

Finally, to account for potential treatment contamination (e.g., use of fentanyl test strips in the control arm, lack of use in the treatment arm), we will employ an instrumental variable approach to estimate the contamination-adjusted intention to treat (CA ITT) effect. We will consider 'receipt of treatment' to be self-reported use of fentanyl test strips at months one, two, or three follow-up visits.

Examine whether the treatment effect is mediated by differential uptake of risk reduction behaviors in the intervention arm (Aim 2). If the RAPIDS intervention shows efficacy in reducing overdose rates among the sample (Aim 1), we will explore the extent to which this relationship works through several possible mediators. For mediation analyses, first, we will examine, in multivariable regression models, which mediators, if any, are significantly changed by the intervention (i.e., the rate of change differed by treatment assignment). For those that are significantly impacted by the intervention, we will conduct path analysis using structural equation modeling to determine whether the effect of the intervention on overdose was through the hypothesized mediator(s). Structural equation modeling (SEM) allows for the simultaneous estimation of total, direct, mediated and indirect effects of a causal variable (i.e., the intervention) on the outcome (i.e., overdose) through a set of mediator variables. SEM can handle outcomes and mediators with a variety of distributions (including, Gaussian, Poisson and Binomial). Inferences for indirect effects can be estimated using bootstrapped confidence intervals.

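### Follow-up items C17 and C18 have lost their last-month gate and have no look-back, so skill1_fu can hold pre-randomisation behaviour and does not match baseline skill1

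*Protocol*

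**What the plan says.** All items are in Protocol Attachment A.

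**Baseline, Section D.** D13 sends anyone who does not agree that they have used a drug containing fentanyl straight to D19. D14 (fentfreq) then asks: "In the last month, how often have you used fentanyl or drugs you were confident contained fentanyl". The item on how the drug was obtained (D17a, fentobt) and D18 (skill1) follow only if D14 shows use. D18 opens: "D18. If fentfreq = 'Once or a couple of times' or 'About once a month' or 'At least every week' or 'Every day".

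**Follow-up, Section C.** C13 (fentfreq_fu) repeats the D14 question and includes *Never*. C14, C15 and C16 are conditional on it. C15 reads "<> 'never' or 'DK/R': The last time you used a drug you were confident contained fentanyl, did you know", and C16 reads "<> 'never' or 'DK/R': The last time you used a drug you were confident contained fentanyl, why were you confident". C17 (fentobt_fu) and C18 (skill1_fu) carry no condition, and C13 has no skip. C18 asks: "The last time you used a drug you were confident contained fentanyl, what did you do when you found out you". Its list offers *DK/R* but nothing for no use since the last visit. C17 lists *No* among the ways the drug was obtained; the baseline item does not.

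**Use in analysis.** SAP section 3, Aim 2, first screens "which mediators, if any, are significantly changed by the intervention (i.e., the rate of change differed by treatment assignment". It does not name skill1_fu.

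**The concern.** A follow-up measure of behaviour should describe behaviour after randomisation. Here a participant with no recent exposure is invited to describe the last one, whenever it was. If that was before enrolment, the answer cannot reflect the intervention, yet it is stored as a follow-up value. The same event can be entered again at each of the five follow-ups listed in Protocol Table 1 (1, 2, 3, 6 and 12 months).

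The C18 answers on throwing the drugs out and on using with someone else around correspond to two of the three target behaviours in Protocol section 3.1b (Behavioral Outcomes). The Aim 2 screen compares rates of change between arms, so baseline and follow-up should measure the same thing in the same people. As printed, skill1 covers last-month users only and skill1_fu covers everyone. A mediator that fails the screen does not go forward to the path analysis, so dilution could drop a real pathway.

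**Working it through.** **1. The two forms side by side**

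| Content | Baseline | Follow-up |
|---|---|---|
| Last-month frequency | D14, after the D13 skip | C13, no skip after it |
| Which drugs | D15, gated | C14, gated |
| Known beforehand | D16, gated | C15, gated |
| Why confident | D17, gated | C16, gated |
| How obtained | D17a (fentobt), gated | C17, **no gate**, *No* added |
| What was done | D18 (skill1), gated | C18 (skill1_fu), **no gate** |

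The wording of D18 has no look-back either. At baseline the last-month window comes only from the gate, so losing the gate loses the window too.

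**2. Who can give a pre-randomisation answer**

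- Use in the last month at C13: the answer is current.
- *Never* at C13 but some use since randomisation: the answer is still post-randomisation. At the 6-month visit this covers use in months 1 to 5; at 12 months, use in months 1 to 11.
- *Never* at C13 and last use before randomisation: the answer is stale.
- Never exposed: there is no event to report, and only *DK/R* fits.

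Only the third group stores pre-randomisation behaviour. Its share, s, is not in the documents and is smaller than the share answering *Never*.

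**3. Equal stale share in both arms**

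Observed rate in an arm = (1 − s) × current rate + s × stale rate. If s and the stale rate are the same in both arms, observed difference = (1 − s) × true difference.

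Inputs: 200 per arm = 250 × 0.80 (SAP section 6). Power is for a two-sided 0.05 test of two proportions, with pooled variance under the null and unpooled under the alternative. As a check on the formula, 20% v 10% at 200 per arm gives 0.802, consistent with the SAP's claim of more than 80%. Assumed here, not in the documents: throwing the drugs out is reported by 20% of control and 35% of intervention among current answers, and by 20% in both arms among stale answers.

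Example, s = 0.25: intervention = 0.75 × 35 + 0.25 × 20 = 31.25%; difference = 11.25 points.

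| s | Ungated difference (points) | Ungated power, 200 per arm | Answers per arm with gate | Gated power, 35% v 20% |
|---|---|---|---|---|
| 0 | 15.0 | 0.92 | 200 | 0.92 |
| 0.10 | 13.5 | 0.87 | 180 | 0.89 |
| 0.25 | 11.25 | 0.73 | 150 | 0.83 |
| 0.50 | 7.5 | 0.42 | 100 | 0.66 |

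At s = 0.50 power falls by 0.50 (0.92 to 0.42). The gate recovers 0.24 (0.42 to 0.66). The other 0.26 is lost because fewer people are exposed, and no branching edit restores it. The gated column assumes that the gate removes exactly the stale answers; a last-month gate would also remove some valid ones at 6 and 12 months.

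**4. Unequal stale shares, no true difference**

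Assume 20% in both arms among current answers, with stale shares of 20% in control and 40% in intervention.

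- Stale rate 10%: control 0.8 × 20 + 0.2 × 10 = 18%; intervention 0.6 × 20 + 0.4 × 10 = 16%. Spurious difference −2 points.
- Stale rate 40%: control 0.8 × 20 + 0.2 × 40 = 24%; intervention 0.6 × 20 + 0.4 × 40 = 28%. Spurious difference +4 points.

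The direction depends on quantities the documents do not give.

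**The case against.** - **Relevance is inferred.** The SAP does not name skill1_fu. The protocol's own examples of behavioural skills are strip confidence, overdose-avoidance practice and giving naloxone, which are other items. F12 records avoidance practices at follow-up, and C34, correctly gated, records the response to a positive strip. Aim 2 runs only if efficacy is shown. This stands and limits the weight of the point. It does not remove it: C34 reaches only people who had a positive strip, and F12 does not ask what was done on finding fentanyl.
- **The form is only the printed form.** Live REDCap branching may already carry the gate. This stands, so checking it comes first.
- **The data are recoverable.** C13 is stored at the same visit. This stands in part: filtering on C13 also discards valid answers about earlier post-randomisation use at 6 and 12 months.
- **Gating has its own cost.** Exposure after randomisation may itself be changed by the intervention, so a comparison among the exposed is not a comparison of the randomised arms. This stands and has to be stated with any gated result.

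A reader might extend the point to C44, "Has fentanyl changed how you use drugs in any of the following ways", which also has no time anchor. The documents do not support that. Baseline D54 has the same unanchored, ungated wording, so nothing was lost between forms, and re-anchoring C44 alone would break its comparability with baseline.

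**Conclusion.** The defect is real on the printed form. C17 and C18 have lost a condition that their baseline counterparts and the three preceding follow-up items carry. skill1_fu can therefore hold pre-randomisation behaviour and is not comparable with baseline skill1. The consequence is dilution of one behavioural item, or bias of either sign if stale shares differ by arm.

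Its size is unknown. The figures above rest on assumed rates and shares and show only how the loss scales.

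Two stronger readings are tempting. One is that the flaw masks any intervention effect. It does not: stale answers arise only when the last use predates randomisation, equal stale shares shrink the contrast without removing it, and the primary overdose outcome does not use C18. The other is to charge all the lost power to the missing gate; in the illustration about half of it would remain with the gate in place.

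This is a modest, cheaply corrected measurement error that matters if skill1_fu enters Aim 2.

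**What to change.** 1. Check the live REDCap branching for C17 and C18. If the gate is there, correct the printed form only.
2. If it is not, choose one of two repairs:
   - put the C14 to C16 condition (fentfreq_fu not *Never* or *DK/R*) on both items, which matches baseline; or
   - anchor both to the period since the last visit, with a response for no such use in that period. This keeps valid use between the 3-, 6- and 12-month visits, but the window is then longer than the baseline one at 6 and 12 months.
3. Delete *No* from C17. Leave C44 as it is.
4. For answers already collected, flag or filter skill1_fu with C13 and report the number exposed in each arm. If skill1_fu is used in Aim 2, say so in the SAP and describe the gated comparison as conditional on post-randomisation exposure.

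The cost is a branching edit or a few words in the form, and one analysis rule. The interview becomes slightly shorter for people not exposed. The downside is fewer answers and a comparison no longer fully protected by randomisation.
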